4.6.6 Telephone Assessments

A brief telephone interview (approximately 10 minutes) will occur if a subject misses a clinic visit but agrees to check-in by telephone to assess AEs, concomitant medication use and the emergence of withdrawal symptoms, to encourage the subject to continue taking investigational products, to verify that the subject is taking the prescribed dose, and to remind the subject of the next scheduled visit and dose increases. A summary of the telephone script follows:

- 1. **AEs:** An open-ended question will be asked as follows: "How have you been feeling since your last clinic visit or phone contact?" If the subject reports a new AE, the resolution of an AE, or a change in the severity of an AE, ask additional questions to determine the severity and dates of occurrence or resolution.
- 2. **CIWA-AR:** Subjects will be assessed for the emergence of withdrawal symptoms using the CIWA-AR. The subject may be asked about changes in drinking status after responses to the CIWA-AR interview indicate significant withdrawal.
- 3. **Concomitant Medications:** Ask the following question: "Have you taken any new medications since you were last seen in the clinic or since our last call? If the subject responds affirmatively, record the name of the medication, the daily dose, route of administration, and reason used. If the medication is contraindicated for the study, then notify a study physician, nurse practitioner, or physician assistant for follow-up with the subject.
- 4. **Drug Compliance:** Verification that the subject is taking the prescribed dose and a reminder to take investigational product and to return the blister card(s) with untaken capsules at the next visit will be made. During the Study Week 1 telephone contact, the subject will be reminded of the drug escalation schedule.
- 5. **Reminders:** Remind the subject of their next scheduled clinic visit, and adjust the date within the visit week if they have a conflict.

4.7 Human Laboratory Paradigm Testing (H-LAB)

During the Randomization/Baseline Visit (prior to taking the study medication) and in Study Week 5, subjects will be seen in-person in the clinic for the human laboratory paradigm testing. The human lab session will last for approximately 45 minutes. Laboratory sessions should occur in the late afternoon if possible. The subject must have BAC = 0.00 prior to starting the H-LAB session. Whenever possible, to ensure that subjects take the capsule on the day of cue reactivity, subjects should either self-report taking their study medication earlier that day or take their study medication while observed by study staff just

before the cue reactivity session. If the subject, for whatever reason, cannot take their study medication that day, they can be rescheduled to complete the cue reactivity paradigm.

After confirmation of eligibility for the H-LAB paradigm, subjects who use nicotine will have the opportunity to use it approximately 1 hour prior to starting the H-LAB paradigm. All subjects will be asked (but not required) to drink 4 oz of water and a restroom break prior to the lab session will be provided. Upon completion of clinical assessments, subjects will be escorted to a comfortable chair in a lighting-controlled, sound-attenuated room for alcohol exposure.

Subjects will be presented with either their *most commonly consumed* alcoholic beverage (e.g. vodka, lager beer) or bottled water. The alcohol or water beverage is presented in the subject's preferred mode of consumption (e.g., small tumbler for vodka, Pilsner glass for beer). Specific alcohol brand preferences are accommodated whenever possible, including choices of mixers (e.g., vodka will be poured into a glass along with orange juice if the favorite drink were a screwdriver).

The H-LAB paradigm will follow our standardized procedures. Audio-recorded instructions ensure standardization within and across subjects. After attaching the physiological monitor (i.e., blood pressure cuff), the session begins with a 3-minute relaxation period that involves subjects sitting quietly and doing nothing. Then a 3-minute water trial begins, in which subjects hold and smell a glass of water as a standard procedure to control for the effects of simple exposure to any potable liquid, including all aspects of stimuli and movement except the nature of the beverage. A second 3-minute relaxation period follows the water trial. Next, subjects hold and smell a glass of their most desired or commonly consumed alcoholic beverage for two consecutive 3-minute alcohol trials. Order of water and alcohol trials is not counterbalanced due to known carryover effects. The water is accompanied by a commercially labeled water bottle and alcohol by the bottle or can from which it was poured and prepared as the teen usually drinks it. Across water and alcohol trials, subjects sniff the beverage for 5 seconds each time a tone sounds: 13 tones sound at variable intervals during each 3-minute block to ensure that all youth receive the same olfactory exposure. Observation via one way window ensures compliance. Subjects rate their alcohol craving after each 3-minute trial.

After every 3 minutes of exposure, each subject will rate his/her urge to drink alcohol using a visual analogue scale (VAS). The primary efficacy endpoint in the H-LAB is the "strength" of alcohol craving measured on a visual analogue scale (VAS; Item 1 below).

Following the H-LAB paradigm, subjects will receive a 7-day supply of the blinded study medication, and the dosing schedule will be reviewed. The subject will be instructed to bring the blister cards with them to the next visit so the project staff can perform drug accountability (capsule counts). The subject will also be instructed to contact project staff if they are experiencing any intolerable adverse events.

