The second primary objective is to leverage a human laboratory paradigm (H-LAB) to evaluate the effects of atomoxetine on an intermediate phenotype (alcohol craving) associated with alcohol use and outcomes in clinical trials. We hypothesize that atomoxetine, as compared to placebo, will decrease the likelihood of craving in the human laboratory during *in vivo* alcohol cue reactivity.

Methodology

This proof-of-concept study is a double-blind, randomized, placebo-controlled, parallel group, single-site clinical trial. After obtaining consent/parent permission/assent, potential subjects and, if younger than 18 years, their parent(s) will complete a medical history and psychiatric diagnosis interview (about the adolescent) to screen for eligibility. Youth will also complete a physical examination, vital signs, drinking history by the timeline follow-back (TLFB) method, alcohol breathalyzer test, Clinical Institute Withdrawal Assessment for Alcohol-revised (CIWA-AR), prior/current medication use, urine toxicology screen, clinical chemistry, and the Columbia Suicide Severity Rating Scale (CSSR-S). Females of child-bearing potential will have a pregnancy test.

If eligible for the study, 50 subjects will be randomized in an approximate 1:1 ratio (targeting 21 subjects per group – 42 subjects total) to either atomoxetine or placebo for 6 weeks.

Atomoxetine will be dosed at 40 mg/day for three days then increased to the maintenance dose of 80 mg (active) taken orally once daily (QD) for an additional 5.5 weeks. Subjects randomized to the placebo condition will be given an equal number of visually matched capsules.

At the randomization/baseline visit and after 4 weeks of investigational product administration (i.e., Study Week 5), subjects will undergo a human laboratory paradigm (i.e., alcohol cue reactivity assessment).

Number of Subjects (Planned): 50 (targeting 21 subjects per group – 42 subjects total)

Main Inclusion/Exclusion Criteria: Subjects will be male and female adolescents, ages 14 to 20 years old, who meet DSM-5 criteria for alcohol use disorder. They must be seeking to reduce their alcohol use.

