2.1 Primary Objectives

- Evaluate the feasibility, acceptability, and tolerability of atomoxetine (40 mg/day for 3 days then 80 mg/day thereafter) plus MET-CBT (i.e., "Path 180") for 6 weeks among adolescents with AUD as confirmed by the Diagnostic and Statistical Manual of Mental Disorders Fifth Edition (DSM-5TM).
- Apply our H-LAB paradigm to evaluate the effects of atomoxetine on intermediate phenotypes associated with alcohol use and outcomes in clinical trials. We hypothesize that atomoxetine, as compared to placebo, will reduce the likelihood of craving in the human laboratory during *in vivo* alcohol cue reactivity.

Study Interventions

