6.1 Feasibility and Acceptability Endpoints

6.1.1 Primary Feasibility Endpoint

The number and percentage of subjects who completed the 6-week active medication phase will determine feasibility.

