6.2 Secondary Outcome: Alcohol Craving Assessed in the H-LAB Paradigm

The secondary endpoint will be alcohol craving assessed during a laboratory alcohol-cue exposure paradigm, at week 5. During the paradigm, participants rated their alcohol craving immediately following exposure to water cues and again immediately following exposure to alcohol cues.

The primary measure of alcohol craving will be the number and percentage of participants who report any level of alcohol craving during a laboratory alcohol-cue exposure paradigm using the following single item: *How strong is your craving to drink alcohol?* Scores range from 0 (None) to 20 (Extremely Strong). Individuals who endorse any level of alcohol craving (e.g., > 1) are considered to experience craving. Individuals who do not report any alcohol craving (e.g., 0) will be regarded as non-craving.

Safety Monitoring Plan

Safety monitoring will be conducted throughout the study; therefore, safety concerns will be identified by continuous review of the data by the principal investigator, clinic staff, medical monitor, and study nurses and physicians.

The Brown University IRB, medical monitor, principal and sub-investigators, and study nurses and physicians will review any safety concerns throughout the trial. In addition, a DSMB will participate in this study.

Quality control is central to all aspects of the activities detailed in this proposal to ensure clinical data accuracy and integrity. Day-to-day oversight of data quality will be delegated to the principal investigator, [name] and/or his designee. With assistance from our core team, he will provide direction with the development of data collection forms, recruitment and tracking databases, data management tasks, and statistical analyses and interpretation. The principal investigator or his designee will oversee the production of standard labels/codebooks for all data collection activities. He or his designee will oversee the production of reports that will track indices of project success, which will be reviewed weekly or biweekly at meetings of our core team, where issues or concerns will be deliberated and corrective action plans put into place.

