8.2 Secondary Outcome: Alcohol Craving Assessed in the H-LAB Paradigm

The secondary endpoint will be alcohol craving assessed during a laboratory alcohol-cue exposure paradigm, at study week 5. During the paradigm, participants rated their alcohol craving immediately following exposure to water cues and again immediately following exposure to alcohol cues. The primary outcome measure will be is the number and percentage of participants who report any level of alcohol craving during a laboratory alcohol-cue exposure paradigm (following exposure to alcohol cues) using the following single item: *How strong is your craving to drink alcohol?* Scores range from 0 (None) to 20 (Extremely Strong). Individuals who endorse any level of alcohol craving (e.g., > 1) are considered to

experience craving. Individuals who do not report any alcohol craving (e.g., 0) will be regarded as non-craving. Using generalized estimating equations, we compared the likelihood of alcohol craving as a function of medication condition.

Quality Control and Quality Assurance

This study will be conducted under International Conference on Harmonization (ICH) Good Clinical Practice (GCP) guidelines and all applicable regulatory requirements.

Actions to ensure the accuracy and reliability of data include the selection of qualified investigators and appropriate study centers; the review of protocol procedures with the investigator and study personnel prior to study start; the design of suitable source documents with appropriate instructions for use; the internal audit of source data according to GCP and internal procedures to ensure their accuracy, completeness, and verifiability; as well as the periodic site monitoring by the Sponsor's representatives (clinical monitors). The Project Coordinator or Project Director will review source documents and CRFs for accuracy and completeness. Any discrepancies will be resolved with the investigator, as appropriate.

Audits and Inspections

Authorized representatives of the Sponsor and the IRB may visit the site to perform audits or inspections, including source data verification. The purpose of the audit or inspection is to systematically and independently examine all study related activities and documents to determine whether these activities were conducted, and data were recorded, analyzed, and accurately reported according to the protocol, GCP guidelines, and any applicable regulatory requirements.

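### The craving cut codes a score of 1 two ways, and H-LAB craving is a primary objective but a secondary endpoint

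*Combined protocol and SAP*

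**What the plan says.** **Rank.** The Synopsis states: "The second primary objective is to leverage a human laboratory paradigm (H-LAB) to evaluate the effects of atomoxetine". Section 2.1 lists the same aim under its primary objectives, with the hypothesis that "atomoxetine, as compared to placebo, will reduce the likelihood of craving in the human laboratory". Section 6.2 then states: "The secondary endpoint will be alcohol craving assessed during a laboratory alcohol-cue exposure paradigm, at week 5". Section 8.2 repeats this ("The secondary endpoint will be alcohol craving assessed during a laboratory alcohol-cue exposure paradigm, at study week 5"), and goes on to call the same variable the primary outcome measure. The endpoints headed as primary in Sections 6 and 8 are feasibility ("The number and percentage of subjects who completed the 6-week active medication phase will determine feasibility", with a target of at least 70% in 8.1.1) and acceptability (at least 80% satisfied on the CSQ-8).

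**Measure.** Section 6.2 states: "The primary measure of alcohol craving will be the number and percentage of participants who report any level of alcohol craving". The item asks how strong the craving is and is scored 0 to 20. Section 4.7 states: "The primary efficacy endpoint in the H-LAB is the 'strength' of alcohol craving measured on a visual analogue scale", and refers to an Item 1.

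**Cut.** Sections 6.2 and 8.2 both state: "Individuals who endorse any level of alcohol craving (e.g., > 1) are considered to experience craving". Both give 0 as the example of non-craving.

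**Analysis.** Section 8.2 plans one comparison of craving: generalized estimating equations (GEE) for the likelihood of craving by medication condition.

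**The concern.** The cut defines the outcome for the only between-arm comparison in Section 8. Two programmers working from the same text could code a score of 1 differently, and both could cite 6.2 in support. With about 21 subjects per arm, a few such scores can visibly change the estimated difference.

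The rank decides how the result may be presented. As written, the same GEE result could be reported as the answer to a primary objective or as a secondary finding, and the plan does not say which.

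**Working it through.** **1. The cut, score by score (Sections 6.2 and 8.2).**
- Score 0: non-craving under the words and under the example.
- Score 1: craving under the words (any level). It is not craving under the numeric example (greater than 1), and it is not the 0 given for non-craving.
- Scores 2 to 20: craving under both.

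If the visual analogue scale allows values between 0 and 1, they fall into the same gap as a score of 1.

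**2. Weight of one subject.** The target is 21 completers per group (Section 1.4), so one recoded subject moves an arm's rate by 1/21 = 4.8 percentage points, two by 2/21 = 9.5 and three by 3/21 = 14.3. If all 50 randomized subjects were rated, 25 per arm, one subject would be 1/25 = 4.0 points. The documents do not say how many subjects are expected to score 1.

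**3. Can one subject change the reading?** This is a constructed example. It assumes one rating per subject, no covariates and a two-sided 0.05 level. The plan states no alpha and does not say which ratings enter the GEE. With one rating per subject and treatment as the only term, the logistic GEE with robust standard error reduces to the ordinary Wald test of the log odds ratio:

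log OR = ln(a/b) − ln(c/d), SE = √(1/a + 1/b + 1/c + 1/d), z = log OR / SE,

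where a and b are the placebo subjects with and without craving, and c and d are the same counts for atomoxetine.

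- Placebo 18/21 vs atomoxetine 11/21: log OR = ln(18/3) − ln(11/10) = 1.792 − 0.095 = 1.696. SE = √(1/18 + 1/3 + 1/11 + 1/10) = 0.761. z = 2.23, p = 0.026.
- One placebo subject scoring 1 is recoded, giving 17/21 vs 11/21: log OR = ln(17/4) − ln(11/10) = 1.447 − 0.095 = 1.352. SE = √(1/17 + 1/4 + 1/11 + 1/10) = 0.707. z = 1.91, p = 0.056.

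Fisher's exact test gives 0.043 and 0.100 for the same two tables. The difference in rates falls from 7/21 = 33.3 points to 6/21 = 28.6 points.

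**4. The rank, side by side.**
- Synopsis: second primary objective.
- Section 2.1: second bullet under the primary objectives.
- Section 6.2: secondary outcome by heading, secondary endpoint by text.
- Section 8.2: secondary outcome by heading, secondary endpoint by text, then primary outcome measure.
- Sections 6.1 and 8.1: the primary endpoints are completion and satisfaction. Each is a percentage set against a target, and neither is a comparison of arms.

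No endpoint labelled primary therefore answers the second primary objective.

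**5. Section 4.7 against 6.2 and 8.2.** Section 4.7 speaks of strength and points to a numbered item. The item in 6.2 and 8.2 asks how strong the craving is. The hypotheses in the Synopsis and 2.1, the endpoint in 6.2 and the analysis in 8.2 all concern the likelihood of any craving. The lead measure can therefore be inferred as any craving after alcohol cues.

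**The case against.** **On the cut.** The number follows an e.g., so the operative rule is any level, and a score of 1 counts as craving. That is probably the intent. But an example that excludes a case the rule includes does not clarify the rule, and it is printed in both the endpoint section and the statistics section. The fair part of the objection is that the worked table was chosen to sit near 0.05. It shows that one subject can matter, not that one will.

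**On rank.** An objective and an endpoint may carry different labels, Sections 6 and 8 both head craving as secondary, and the same GEE is run either way. It is true that no calculation changes. What changes is the status of the result, and 8.2 uses both words for one variable.

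**On 4.7.** A reader might infer that the graded strength score is a rival primary endpoint. The documents do not support that. Read with the item wording in 6.2, Section 4.7 most naturally identifies which scale item is used, and every statement of hypothesis, endpoint and analysis points to any craving.

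**On the graded score.** No analysis of the 0–20 score is planned, and a reader might infer that the yes/no outcome costs this trial power. The documents cannot show that, because they give no craving rate, standard deviation, correlation or expected effect. A yes/no outcome misses a fall that stops short of zero, but it can do better than the score if the drug mainly moves subjects to zero. One binary measure that matches the stated hypothesis is a legitimate choice.

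**Conclusion.** Two points are wrong as written. The cut in 6.2 and 8.2 assigns a score of 1 to craving by its words and excludes it by its number, and each such subject is worth 4.8 points at 21 per arm. H-LAB craving is primary in the Synopsis and 2.1 but secondary in 6.2 and 8.2, which leaves the second primary objective without a primary endpoint. Both are established from the text alone. The p-values in the example rest on an assumed 0.05 level, one rating per subject and constructed counts, and they predict nothing about this trial's result.

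The wording in 4.7 is a minor ambiguity. The absence of an analysis of the 0–20 score is not an error.

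**What to change.** 1. In 6.2 and 8.2, define craving as a score above 0 and non-craving as a score of 0, and delete the conflicting example.
2. Give H-LAB craving one rank, stated identically in the Synopsis, 2.1, 6.2 and 8.2, and remove the second label within 8.2.
3. Reword the sentence in 4.7 so that it names the scale item and refers to the any-craving endpoint in 6.2.
4. Optional: add a supportive Week 5 analysis of the 0–20 alcohol-cue score, adjusted for the baseline H-LAB score. Label it post hoc if outcome data have been seen.

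Items 1 to 3 are wording changes in five places and need no new visits, subjects or measurements. Item 4 is one extra model on ratings already collected. Its cost is a second craving result that may disagree with the lead one.

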4.8 Final Clinic Visit (End of Study Visit)

The final in-clinic assessment will occur at the end of (or immediately following) the active treatment phase, **typically Study Week 6**, **Day 7**. This visit should occur after the subject takes the last dose of study drug. Subjects will complete the Client Satisfaction Questionnaire - 8 (134), an instrument used to assess patients' satisfaction with psychiatric treatment (135, 136). If a subject withdraws from the study early for any reason, the subject will be asked to return to the clinic for the conduct of the final clinic visit assessments.

4.9 Telephone Follow-up Assessments

Subjects will be contacted by telephone for a follow-up interview 2 weeks after the final in-clinic visit. During this 2-week follow-up interview, the subject will be asked about any ongoing AEs that they may have been experiencing at the last clinic visit and any newly emerged medical conditions/AEs since that visit. To prompt reporting of new AEs, the subject will also be asked about any ongoing or new medication use.

4.10 Conducting Sessions Remotely

Study visits may be conducted remotely, when necessary. By limiting in-person contact, allowing remote sessions may effectively decrease COVID-19-related risks. At the study physician's discretion, the physical exam may be conducted via the Brown University HIPAA-compliant Zoom platform (either in an adjacent room or remotely). Research staff still need to collect vital signs, weight, a urine toxicology drug screen, and a urine pregnancy best (if biological sex at birth is female) in person (prior to the physical exam). Blood chemistry and related tests must be done at a local laboratory.

For weekly visits, Zoom video conferencing will be used to conduct the session for those items amenable to remote collection. Extra medication will be mailed from participants to the laboratory via pre-paid postal mail. When remote sessions are held, biospecimen collection will not be done. Even so, to capture biospecimens on a regular basis, no two consecutive post-randomization weekly checkups may be done remotely unless approved beforehand by a study physician.

Dose-Adjustment Criteria

